The primary endpoint is the pharyngeal cure rate – that is, the proportion of subjects who return for TOC who clear their infections as evidenced by a negative culture 4-7 (+/-1) days after treatment. Persons who test negative for NG at their enrollment visit (i.e. infection cleared between initial clinical screening test and enrollment) will be excluded from analysis. Treatment failure will be defined as a positive culture 4-7 (+/-1) days after treatment. The cure rate will be calculated as the number of cured subjects divided by the total number of subjects who received treatment and returned for follow-up testing in a modified an intention to treat (mITT) analysis. We will also calculate the 95% CI for this proportion.

We will conduct an interim analysis after we have primary outcome results for 25 subjects. If the cure rate is $\leq 44\%$ (99% CI 17% – 74%; i.e. 12 persons of 25 persons with a positive culture on treatment date fail treatment), we will stop the study. We will also monitor for renal toxicity at the interim analysis. We plan to obtain pre-treatment and post-treatment Creatinine. Increases $>40\%$ will be considered significant. If more than 20% of the study population has a $>40\%$ increase in serum Creatinine, we will halt the study. We chose 20% because if 20% of subjects experience renal toxicity it is unlikely to be due to chance (95% CI 7 – 40%). For our second objective, we will compare the MIC of cures to treatment failures using a stratified approach (Table 2), and we will correlate this data with individual peak gentamicin level in order to estimate the ideal pharmacodynamic (PD) criterion (Obj. 2). For persons who fail treatment we will also compare the pre- and post-treatment genatmicin MIC to estimate whether single dose gentamicin therapy can “induce” resistance (Obj. 3) as an exploratory analysis. We will consider an increase in the MIC by two doubling-dilutions (i.e. from MIC of 2 to 8 $\mu\text{g/mL}$, or 8 to 32 $\mu\text{g/mL}$) to represent induced resistance, and we will calculate the

proportion of isolates among those that fail treatment that demonstrate induced resistance following receipt of gentamicin. Lastly, we will report the number and proportion of subjects who report side effects.

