Related: The AE is clearly related to the study procedures.

AEs are identified at the TOC visit using the symptom screen, and with Creatinine monitoring.

SAEs and specific procedure-associated AEs are reported to the Medical Monitor within 24 hours. In addition, all AEs are reported according to the University of Washington AE reporting guidelines.

MANAGEMENT OF RISKS TO SUBJECTS

Expected AEs

Expected AEs associated with gentamicin include:

- Pain at injection site
- Bruising at injection site

AE Management

- Warm compresses as needed
- Tylenol as needed

DATA ANALYSIS PLANS

The Medical Monitor will conduct interim analyses after we have primary outcome results for 10 and 25 subjects. (Enrollment will pause until analyses can be conducted). Stopping rules include the primary end point (i.e. pharyngeal cure rate), and adverse events. If after 10 and 25 subjects, the cure rate is $\leq 44\%$ (99% CI 17% – 74%; i.e. 11 persons of 25 persons with a positive culture on treatment date fail treatment), we will stop the study. We chose these numbers using the O'Brien-Fleming method of alpha spending for multiple analyses, assuming an alpha of 0.003 for the first analysis and an alpha of 0.049 for the final analysis. Using the 99% CI obtained with 11/25 treatment failures, the upper bound is less than 75%. (Our hypothesis is that gentamicin alone will be 80% effective for pharyngeal gonorrhea, with the goal to use it in combination with a second agent). Alternatively, if at interim analysis more than 20% of subjects (99% CI 20% - 46%) have a greater than 40% increase in their creatinine from baseline, we will halt the study.

Data Analysis

The proposed study aims to evaluate the efficacy of a single intramuscular (IM) dose of 360 mg of gentamicin in the treatment of pharyngeal gonorrhea. Secondary objectives include evaluating the renal safety and tolerability of 360mg of gentamicin, *documenting peak serum gentamicin levels by subject weight*, and estimating the ideal pharmacodynamic criterion using a combination of peak gentamicin concentration levels compared to MIC and treatment outcomes. *In exploratory analyses*, we will attempt to determine whether gentamicin-monotherapy induces antimicrobial resistance among treatment failures. The specific aims are:

- 1) Determine the proportion of persons whose pharyngeal gonococcal infections are cured with a single dose of 360mg gentamicin intramuscularly alone.

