- 2) Evaluate the renal safety and tolerability of 360mg IM of gentamicin.
- 3) Document mean peak gentamicin levels following 360mg IM of gentamicin stratified by weight.
- 4) Estimate the best pharmacodynamics criterion (i.e. peak/MIC ratio) for pharyngeal gonorrhea treated with gentamicin *using individual* and mean peak gentamicin levels and NG isolate MIC.
- 5) Among treatment failures, *conduct exploratory analyses* comparing pre- and post-treatment MIC for evidence of induced resistance.

Analyses

The primary endpoint is the pharyngeal cure rate – that is, the proportion of subjects who return for TOC who clear their infections as evidenced by a negative culture 4-7 (+/-1) days after treatment. The cure rate will be calculated as the number of cured subjects divided by the total number of subjects who received treatment and returned for follow-up testing in a modified an intention to treat (mITT) analysis. We will also calculate the 95% CI for this proportion.

$$\text{Cure rate} = \frac{\text{number of subjects with negative pharyngeal culture at TOC}}{\text{number of subjects with + throat test at enrollment \& received gentamicin}}$$

Persons who test negative for NG at their enrollment visit (i.e. infection cleared between initial clinical screening test and enrollment) will be excluded from analysis. Treatment failure will be defined as a positive culture 4-7 (+/-1) days after treatment.

For our second objective, we will obtain pre- and post-treatment serum creatinine. An elevation of >40% will be considered significant. We will evaluate subject's tolerability (Obj. 2) using a standardized symptom questionnaire (see Appendix F) conducted at the TOC visit. The symptoms questioned will include, but not be limited to, rash, tinnitus, decreased hearing, nausea, vomiting, diarrhea, headaches, and decreased appetite. There will also be a section for free response.

Our third objective is to document the pharmacokinetics of 360mg of IM gentamicin by weight. We will obtain serum gentamicin levels at 30, 45 and 60minutes post dosing based on previous studies that estimated that IM gentamicin peaks between 30-60 minutes post-dose.

We will stratify the results by time post-dose, as well as by subject weight in kilograms (categorized).

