As a means to preserve funding and ensure safety, we will conduct interim analyses after we have primary outcome results for 10 and 25 subjects. (Enrollment will pause until analyses can be conducted). Stopping rules include the primary end point (i.e. pharyngeal cure rate), and adverse events. If after 25 subjects, the cure rate is $\leq 44\%$ (99% CI 17% – 74%; i.e. 11 persons of 25 persons with a positive culture on treatment date fail treatment), we will stop the study. We chose these numbers using the O'Brien-Fleming method of alpha spending for multiple analyses, assuming an alpha of 0.003 for the first analysis and an alpha of 0.049 for the final analysis. Using the 99% CI obtained with 11/25 treatment failures, the upper bound is less than 75%. Alternatively, if at interim analysis 32% or more of subjects (99% CI 9.4% - 63%) have a greater than 40% increase in their creatinine from baseline, we will halt the study.

Appendices

- A. Clinician Information and Referral Script
- B. Study Info Card
- C. Appointment Reminder Card
- D. Screening Eligibility Form
- E. Enrollment visit data entry form
- F. TOC visit data entry form

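### The interim efficacy stopping rule equates a cure rate of 44% or less with 11 (or 12) failures of 25, but 44% cured is 14 failures

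*Combined protocol and SAP*

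**What the plan says.** The efficacy stopping rule appears in three places, each time with the threshold of 44% cured and an interval of 17% to 74% labelled 99%.

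- **Statistical Analysis Plan (opening summary):** the threshold is explained as "i.e. 12 persons of 25 persons with a positive culture on treatment date fail treatment".
- **Data Analysis Plans (within the Data Safety and Monitoring Plan):** the count becomes "i.e. 11 persons of 25 persons with a positive culture on treatment date fail treatment". This version applies the threshold at two looks: "If after 10 and 25 subjects, the cure rate is $\leq 44" percent.
- **Data Analysis, Analyses:** the count is again 11 failures, but the threshold is given for 25 subjects only.

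The last two sections give the same reason for the boundary: "Using the 99% CI obtained with 11/25 treatment failures, the upper bound is less than 75" percent. They also give the error rates: "assuming an alpha of 0.003 for the first analysis and an alpha of 0.049 for the final analysis". The monitoring section adds the expected effect: "Our hypothesis is that gentamicin alone will be 80% effective for pharyngeal gonorrhea".

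On definitions, cure is a negative culture at the test-of-cure (TOC) visit, and "Treatment failure will be defined as a positive culture 4-7 (+/-1) days after treatment". Among subjects with a primary outcome result, cure and failure are therefore complements.

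**The concern.** The percentage and the counts cannot both be the rule. A cure rate of 44% in 25 subjects leaves 14 failures, not 11 or 12, and the two counts also disagree with each other. It looks as though the number cured (11) was written as the number failing.

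This is the trial's only efficacy stopping rule, and enrolment pauses while it is applied. A reader who follows the failure count stops at 56% or 52% cured; a reader who follows the percentage stops only at 44%. If 11, 12 or 13 subjects fail, the Medical Monitor would have to choose between the readings after seeing the data, which a prespecified rule is meant to prevent.

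**Working it through.** **Inputs.** n = 25; threshold 44% cured; printed interval 17% to 74%, labelled 99%; upper bound required below 75%; first-analysis alpha 0.003; hypothesised cure rate 80%. All come from the sections cited above.

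**Step 1: counts.** Cured = 25 − failures.

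- 0.44 × 25 = 11 cured, so 25 − 11 = 14 failures.
- 11 failures: 14/25 = 56% cured.
- 12 failures: 13/25 = 52% cured.

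**Step 2: reproduce the printed interval.** The plan names no method. For x cured of n, the exact (Clopper-Pearson) limits are L = the α/2 quantile of Beta(x, n − x + 1) and U = the 1 − α/2 quantile of Beta(x + 1, n − x).

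| Cured / failed | Exact 99% CI | Exact 99.7% CI (α = 0.003) |
|---|---|---|
| 11 / 14 (44%) | 19.74%–70.54% | 17.05%–73.81% |
| 12 / 13 (48%) | 22.83%–73.93% | 19.94%–77.01% |
| 13 / 12 (52%) | 26.07%–77.17% | 22.99%–80.06% |
| 14 / 11 (56%) | 29.46%–80.26% | 26.19%–82.95% |

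Of these, only 11 cured at 99.7% gives 17% to 74%. It also agrees with the alpha of 0.003 and the bound below 75%. The 99% label is therefore wrong.

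The creatinine rule in the same paragraph of Analyses shows the same mislabelling. Its interval for 32% (8/25) is printed as 99%, 9.4% to 63%. The exact 99.7% interval is 9.38% to 63.24%; the exact 99% interval is 11.35% to 59.52%.

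**Step 3: test the stated reason at the stated count.** With 11 failures (14 cured), the 99% upper bound is 80.3% exact, 77.5% Wilson, 77.5% Agresti-Coull, 78.7% Jeffreys and 81.6% Wald. None is below 75%. With 12 failures (13 cured), the exact 99% bound is 77.2%, also above 75%.

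**Step 4: decision under each reading.** Each count is read as that many failures or more.

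| Failures of 25 | Cured | 44% or less cured | 12 fail | 11 fail |
|---|---|---|---|---|
| 10 | 60% | continue | continue | continue |
| 11 | 56% | continue | continue | stop |
| 12 | 52% | continue | stop | stop |
| 13 | 48% | continue | stop | stop |
| 14 | 44% | stop | stop | stop |

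**Step 5: probability of stopping at 25.** P(X ≤ c), with X the number cured, binomial(25, true cure rate), and c = 11, 13 or 14.

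| True cure rate | 44% or less (c = 11) | 12 fail (c = 13) | 11 fail (c = 14) |
|---|---|---|---|
| 80% | 0.008% | 0.15% | 0.56% |
| 75% | 0.09% | 1.1% | 3.0% |
| 70% | 0.6% | 4.4% | 9.8% |
| 60% | 7.8% | 26.8% | 41.4% |
| 50% | 34.5% | 65.5% | 78.8% |

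At a true 60%, the 11-failure reading stops about five times as often as the percentage (41.4 / 7.8 = 5.3).

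**The case against.** The percentage is the operative criterion. It and its interval are the same in all three places, and the counts are only parenthetical glosses, so a careful reader would follow the percentage. A Medical Monitor also reviews the data before any recommendation. This lowers the risk of misapplication but does not remove it: the rule says the study will stop, and the sentence giving the reason is itself built on the failure count.

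Some side conclusions depend on the interval method. For 12 failures, the 99% Wilson and Agresti-Coull upper bounds are 74.5%, which would meet the 75% criterion. For 11 failures, whether 80% is excluded is close: the exact bound is 80.3%, but Wilson, Agresti-Coull and Jeffreys bounds fall below 80%. Both points stand as qualifications. However, the printed figures reproduce with the exact 99.7% method, and the 11-failure version misses 75% by every method tried.

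If the cure rate is the hypothesised 80%, every version stops with probability below 0.6%. That is true, but a futility rule matters at lower cure rates, and the Executive Summary itself says efficacy at the pharynx may be below that at genital sites.

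Finally, correcting the count at 25 leaves the look at 10 subjects unsettled. This also stands. The monitoring section applies the threshold at 10, Analyses schedules that look but gives the threshold only at 25, and the summary and Monitoring Procedures have a single look at 25. Linking alpha 0.003 to the look at 25 is therefore an inference from the matching interval.

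**Conclusion.** The concern holds. The rule as written gives three thresholds for one decision: 44%, 52% and 56% cured. The 11-failure version fails the plan's own criterion by every method checked; the 12-failure version fails it under the exact method. The readings disagree at 11 to 13 failures. At a true 60% cure rate, the chance of stopping at 25 ranges from 7.8% to 41.4%; at 80% it stays below 0.6%.

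The counts and percentages are plain subtraction and need no assumption. The inference that 11 cured was intended assumes exact intervals at alpha 0.003, which the printed figures support. The stopping probabilities assume independent binomial outcomes in 25 evaluable subjects and leave out any look at 10. This should be corrected before the rule is used.

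**What to change.** State the rule once, as a count, and use the same words in the opening Statistical Analysis Plan, the Data Analysis Plans of the monitoring section, and Analyses.

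- The plan's 44%, 17% to 74%, alpha of 0.003 and bound below 75% all agree on this: stop if 11 or fewer of 25 evaluable subjects are cured (14 or more failures), with the interval at the boundary labelled exact 99.7%. The sponsor should confirm that this was intended.
- Delete the clauses that give 11 or 12 failures, and rewrite the rationale sentence in terms of 11 of 25 cured.
- If a true 99% interval is preferred, the largest number cured with an exact upper bound below 75% is 12 of 25 (13 failures; upper bound 73.9%). The percentage then becomes 48%.
- In the same edit, say whether an efficacy rule applies at 10 subjects and which look carries alpha 0.003. At 10 subjects, 44% or less means 4 or fewer cured. The exact 99% upper bound for 4/10 is 80.9%, so the present rationale does not carry over to that look.

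The cost is protocol wording in three places. No patients, visits or procedures are added.

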The proposed study aims to evaluate the efficacy of a single intramuscular (IM) dose of gentamicin in the treatment of pharyngeal gonorrhea. Secondary objectives include documenting the efficacy stratified by minimal inhibitory concentration (MIC) compared with the gentamicin peak level in order to estimate a pharmacodynamic criterion. We will also attempt to determine whether gentamicin monotherapy induces antimicrobial resistance among treatment failures. Lastly, we will evaluate the tolerability of 360 mg of IM gentamicin, stratified by subject weight (i.e. weight based dosing). The specific aims are:

- 1) Determine the proportion of persons whose pharyngeal gonococcal infections are cured with a single dose of 360mg gentamicin intramuscularly alone.
- 2) Evaluate the *renal safety* and tolerability of 360mg IM of gentamicin.
- 3) Document mean peak gentamicin levels following 360mg IM of gentamicin stratified by weight.
- 4) Estimate the best pharmacodynamics criterion (i.e. peak/MIC ratio) for pharyngeal gonorrhea treated with gentamicin using individual and mean peak gentamicin levels and NG isolate MIC.
- 5) Among treatment failures, conduct exploratory analyses comparing pre- and post-treatment MIC for evidence of induced resistance.

Study Design: Prospective cohort

Study Population & Inclusion Criteria:

Persons diagnosed with pharyngeal gonorrhea who are not yet treated

Exclusion criteria:

- Age less than 16 years
- Receipt of antibiotics in ≤ 30 days
- Known allergy to any aminoglycoside
- History of renal disease (including diagnosis of solitary kidney, chronic renal insufficiency, renal cell carcinoma etc),
- Use of concurrent nephrotoxic drugs or muscle relaxants
- History of diabetes
- History of hearing loss or tinnitus
- Concurrent infection with syphilis or chlamydia
- Pregnancy and/or nursing
- Unable to return for a follow-up visit 4-7 days (+/- 1 day).
- Study team's discretion

Intervention: 360mg IM gentamicin x 1

Primary Outcome: Negative gonorrhea culture 4-7 days (+/- 1 day) after treatment

Sample Size: 60 persons

Statistical Analysis Plan:

[figure not shown]

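### Two interim intervals labelled 99% are exact 99.7% intervals, a third matches neither level, and the evaluable number behind the interim alpha of 0.003 is not stated

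*Combined protocol and SAP*

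**What the plan says.** The efficacy rule stops the study at a cure rate of 44% or less among 25 subjects. In the Analyses part of Data Analysis, and in Data Analysis Plans within the monitoring plan, it is supported by "99% CI 17% – 74%; i.e. 11 persons of 25 persons with a positive culture on treatment date fail treatment". The Statistical Analysis Plan near the front prints the same interval with the same 99% label. Both later sections attribute the numbers to O'Brien-Fleming spending and give its levels: "assuming an alpha of 0.003 for the first analysis and an alpha of 0.049 for the final analysis". They then add: "Using the 99% CI obtained with 11/25 treatment failures, the upper bound is less than 75" (per cent).

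The renal rule appears with two different intervals, both labelled 99%. Analyses has "if at interim analysis 32% or more of subjects (99% CI 9.4% - 63" (per cent). Data Analysis Plans has "more than 20% of subjects (99% CI 20% - 46" (per cent).

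The only stated size is "Sample Size: 60 persons", which is a number enrolled. The primary analysis leaves out subjects who test negative at enrolment and those who do not return. The peak/MIC paragraph works with n=40 at an 80% cure rate. No section gives an information fraction or a planned evaluable number.

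**The concern.** An alpha of 0.003 corresponds to a 99.7% interval, while a 99% interval corresponds to an alpha of 0.01. The paragraph names both levels as if they were one. The intervals are the printed justification for the stopping rules, so a Medical Monitor or reader should be able to recompute them from the label. At present they cannot.

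The alpha has a similar gap. An O'Brien-Fleming-type level depends on the fraction of information available at the look. The look is counted in subjects with a primary outcome, but the total it is a fraction of is not given. Taking 25 of the stated 60 does not return 0.003.

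**Working it through.** **Inputs.** 11/25 (44%) and 8/25 (32%) from Analyses; 5/25 (20%) for the rule in Data Analysis Plans; alpha 0.003 and 0.049; 60 enrolled; n=40 at 80% cure. Assumption: the alphas are two-sided within an overall 0.05, since the plan does not state sidedness.

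**Step 1, interval level.** The exact (Clopper-Pearson) limits for x of n at level 1−α are the α/2 quantile of Beta(x, n−x+1) and the 1−α/2 quantile of Beta(x+1, n−x).

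| Count | Printed as 99% | Exact 99% | Exact 99.7% |
|---|---|---|---|
| 11/25 | 17 to 74 | 19.7 to 70.5 | 17.05 to 73.81 |
| 8/25 | 9.4 to 63 | 11.3 to 59.5 | 9.38 to 63.24 |
| 5/25 | 20 to 46 | 4.6 to 47.0 | 3.5 to 51.0 |

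The first two printed intervals reproduce at 99.7% to the printed precision. At 99%, the Wilson, Wald, Agresti-Coull and Jeffreys methods do not reproduce 17 to 74 either. The third printed interval fits neither level: its lower limit of 20% equals the observed proportion 5/25, so it cannot be an interval around that proportion.

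**Step 2, alpha.** O'Brien-Fleming-type (Lan-DeMets) spending for an overall two-sided 0.05 is α(t) = 4[1 − Φ(2.2414/√t)].

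- t = 25/50: 2.2414/0.7071 = 3.170, so α = 0.00305. The final level from the bivariate normal is 0.0490. This is the plan's pair.
- t = 25/60: 2.2414/0.6455 = 3.472, so α = 0.00103. The final level is 0.0497.

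Other forms at 25/60 also miss 0.003: the classical two-look boundary gives 0.0023/0.0491, and the spending form 2[1 − Φ(1.96/√t)] gives 0.0024. The look at 10 subjects in two of the sections spends about 0.000001 or less and leaves the level at 25 unchanged.

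**Step 3, where 50 may come from.** If n=40 is the number cured at 80%, then 40/0.80 = 50 evaluable. By contrast, 80% of 60 is 48. This is an inference; 50 is never stated.

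**Step 4, effect on the boundary.** Suppose a reader takes the boundary to be the largest number cured of 25 whose upper limit is below 75%.

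- At 99.7%: 11 cured (upper limit 73.8%; 12 gives 77.0%). This is the printed 44%.
- At 99%: 12 cured (upper limit 73.9%; 13 gives 77.2%).

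The binomial chance of stopping with at most 11 versus at most 12 cured is 34.5% versus 50.0% if true cure is 50%, and 7.8% versus 15.4% if it is 60%. At the hypothesised 80% both are below 0.04%.

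**The case against.** The strongest reply is that the operative rule is the printed threshold, 44% or less at 25, and this is 11 cured whatever the interval is called. The sentence about the 75% bound is true at either level, since the upper limit for 11/25 is 70.5% at 99% and 73.8% at 99.7%. No section says that the boundary is the largest count meeting that criterion. This stands: correcting the label changes no decision under the printed rule, and the stopping probabilities in step 4 apply only to a reader who rebuilds the rule at the labelled 99%.

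It is also fair to say that 60 is enrolment rather than information, and that 25 of about 50 evaluable is the natural reading. This stands too, and reduces the alpha point to an unstated evaluable number.

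A reader might go further and infer that the plan's own levels give three stopping counts: 12, 11 and 10. The documents do not support this. They state two levels, 99% and alpha 0.003. The count of 10 needs an alpha of about 0.001, which appears nowhere; it requires both 60 as the information total and Lan-DeMets spending (upper limit for 10/25 73.1%, for 11/25 76.3%). With the classical boundary at 25/60 the count is 11 again (upper limit 74.5%).

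The reply does not touch the labels themselves. Two printed intervals match 99.7% and not 99%, and a third matches neither.

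**Conclusion.** The point holds as a labelling error and an omission. The 17% to 74% interval (in three sections) and the 9.4% to 63% interval (in Analyses) are 99.7% intervals printed as 99%. For 11/25 the upper limit shown is about 3 points above the true 99% limit (73.8% against 70.5%). The monitoring plan's renal interval is wrong at either level for 5/25, so it would be a mistake to infer that every interval labelled 99% is simply a 99.7% one. The 0.003/0.049 pair is correct for 25 of 50 evaluable and not for 25 of 60; the plan needs to say which total it rests on.

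A reader might also infer that the mislabelling alters when the study stops. It does not, provided that alpha 0.003 is kept: the 44% boundary already agrees with that level. The interval result assumes exact limits. The alpha result assumes Lan-DeMets spending with a two-sided overall 0.05.

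A separate conflict remains. A 44% cure rate is 11 cured and 25 − 11 = 14 failing, but two sections say that 11 fail and the front section says 12 fail. Relabelling the intervals does not resolve this.

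**What to change.** 1. In the Statistical Analysis Plan, Data Analysis Plans and Analyses sections, relabel 17% to 74% as a 99.7% interval. In Analyses, do the same for 9.4% to 63%.
2. In Data Analysis Plans and Analyses, change the sentence about the upper bound below 75% to refer to the 99.7% interval, and say that it matches alpha 0.003.
3. Recompute the renal interval in Data Analysis Plans, giving the count it belongs to, and reconcile that passage with the renal rule in Analyses.
4. State the evaluable number on which 0.003/0.049 rests (50, if that is what was meant). If another number is intended, recompute the alpha and check that the printed boundary still follows.
5. Separately, reconcile the cured and failed counts in the three sections.

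Items 1 to 4 cost wording and a short recalculation. They add no patients and no procedures.

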The Medical Monitor, [name], will review study conduct including efficacy and renal toxicity and AEs in aggregate on at a single interim analysis after 25 subjects, and at the end of the study. The Medical Monitor will review serious adverse events (SAEs), hearing loss, and serious drug allergies in real-time. Study data are provided to the Medical Monitor prior to the interim and final analysis. Data reports are prepared by the PI, [name].

MONITORING REPORT

The Medical Monitor, [name], will provide a written report to the study team with recommendations for study modification, study continuation/discontinuation as relevant. The study team is responsible for forwarding the report to the IRB.

COLLECTION AND REPORTING OF SAEs AND AEs

For this study, the following standard AE definitions are used:

Adverse event: Any unfavorable and unintended sign (including an abnormal laboratory finding), symptom or disease temporally associated with the use of a medical treatment or procedure, regardless of whether it is considered related to the medical treatment or procedure.

Serious Adverse Event: Any AE that results in any of the following outcomes:

- Death
- Life-threatening
- Event requiring inpatient hospitalization or prolongation of existing hospitalization
- Persistent or significant disability/incapacity

AEs are graded according to the following scale:

Mild: An experience that is transient, & requires no special treatment or intervention. The experience does not generally interfere with usual daily activities. This includes transient laboratory test alterations.

Moderate: An experience that is alleviated with simple therapeutic treatments. The experience impacts usual daily activities. Includes laboratory test alterations indicating injury, but without long-term risk.

Severe: An experience that requires therapeutic intervention. The experience interrupts usual daily activities. If hospitalization (or prolongation of hospitalization) is required for treatment it becomes an SAE.

The study uses the following AE attribution:

Not related: The AE is clearly not related to the study procedures (i.e., another cause of the event is most plausible and/or a clinically plausible temporal sequence is inconsistent with the onset of the event).

Possibly related: An event that follows a reasonable temporal sequence from the initiation of study procedures, but that could readily have been produced by a number of other factors.

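### The renal-toxicity halting threshold is above 20% in two sections and 32% or more in a third, so 6 or 7 of 25 subjects draws opposite instructions

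*Combined protocol and SAP*

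**What the plan says.** The renal event is the same throughout: a rise in serum creatinine of more than 40% over baseline (Data Analysis, Analyses: "An elevation of >40% will be considered significant"). The action is also the same, namely halting the study. The threshold is not.

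- **Statistical Analysis Plan at the front of the protocol:** "If more than 20% of the study population has a" creatinine rise of that size, the study is halted. The section defends the figure: "if 20% of subjects experience renal toxicity it is unlikely to be due to chance (95% CI 7 – 40"%).
- **Data Safety and Monitoring Plan, Data Analysis Plans:** the study is halted "if at interim analysis more than 20% of subjects (99% CI 20% - 46%) have a greater than 40% increase in their creatinine".
- **Data Analysis, Analyses (last paragraph):** the study is halted "if at interim analysis 32% or more of subjects (99% CI 9.4% - 63%) have a greater than 40% increase in their creatinine".

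The timing of the looks differs as well. The front section says "We will conduct an interim analysis after we have primary outcome results for 25 subjects", and Monitoring Procedures has the medical monitor review "efficacy and renal toxicity and AEs in aggregate on at a single interim analysis after 25 subjects". The two later sections plan looks at 10 and at 25 subjects.

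**The concern.** This is the only numeric safety stopping rule in the documents, and renal safety is a named aim. Such a rule is useful because the decision is fixed before the data are seen. Here, for some results, the decision depends on which section is read. Following the 32% version at 6 or 7 events would breach the other two sections. Following the 20% version would stop a study that the Data Analysis section allows to continue. The investigator prepares the interim data report, so a threshold settled after the count is known would be open to challenge.

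**Working it through.** **1. Are these two rules, or one rule with a typing error?** I reproduced the plan's own intervals with exact (Clopper-Pearson) limits, where the lower limit is the α/2 quantile of Beta(x, n−x+1) and the upper limit is the 1−α/2 quantile of Beta(x+1, n−x).

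| Section | Stated | Count that fits | Recomputed |
|---|---|---|---|
| Front Statistical Analysis Plan | 20%, 95% CI 7–40% | 5/25 | exact 95%: 6.8%–40.7% |
| Data Analysis | 32%, 99% CI 9.4%–63% | 8/25 | exact 99.7%: 9.4%–63.2% (exact 99%: 11.3%–59.5%) |
| Monitoring plan | >20%, 99% CI 20%–46% | 6/25, probably | Wald 99%: 2.0%–46.0% |

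The 32% figure reproduces as 8/25 at 1 − 0.003 = 99.7%, which matches the interim alpha of 0.003 in the same paragraph. That paragraph's efficacy interval (17%–74%) is also the exact 99.7% interval for 11/25 (17.1%–73.8%). So 32% looks deliberately derived, and 20% carries its own rationale: these are two rules.

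For the monitoring plan, 0.24 ± 2.576 × √(0.24 × 0.76 / 25) = 0.24 ± 0.220, which gives 2.0%–46.0%. The printed lower limit of 20% has probably lost a decimal point. Neither labelling matter changes when the study halts.

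**2. Counts on which the rules disagree** (x/n > 0.20 but x/n < 0.32).

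- n = 25: more than 20% means x > 5, so 6 or more. 32% or more means x ≥ 8. They disagree at 6 (24%) and 7 (28%). Results of 0–5 and of 8 or more give the same decision.
- n = 10: more than 20% means x > 2, so 3 or more. 32% or more means x ≥ 3.2, so 4 or more. They disagree at 3 (30%).

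**3. How often this would matter.** The documents give no expected rate of a >40% rise, so the true rate p is an assumed range. With X ~ Binomial(25, p):

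| p | P(X ≥ 6) | P(X ≥ 8) | P(X = 6 or 7) |
|---|---|---|---|
| 5% | 0.1% | <0.1% | 0.1% |
| 10% | 3.3% | 0.2% | 3.1% |
| 15% | 16.2% | 2.5% | 13.6% |
| 20% | 38.3% | 10.9% | 27.4% |
| 25% | 62.2% | 27.3% | 34.8% |
| 30% | 80.7% | 48.8% | 31.8% |

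**4. If the rule also applies at 10 subjects.** P(exactly 3 of 10) is 1.0%, 5.7%, 20.1% and 26.7% at p = 5%, 10%, 20% and 30%. For the overall chance of halting I summed over X₁ ~ Bin(10, p) and X₂ ~ Bin(15, p), halting if X₁ ≥ 3 or X₁ + X₂ ≥ 6, against X₁ ≥ 4 or X₁ + X₂ ≥ 8. The results are 1.2% against 0.1% at p = 5%, 8.7% against 1.4% at 10%, 47.9% against 17.8% at 20%, and 84.8% against 56.2% at 30%.

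**The case against.** The strongest points on the other side are these.

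- **Denominator.** The look is triggered by primary outcome results for 25 subjects. Those found culture-negative at enrolment leave the efficacy analysis, yet they have been dosed and had blood drawn. The renal denominator could therefore exceed 25. This stands as a qualification. With 26 to 28 subjects the conflicting counts are 6–8, and with 30 they are 7–9. The conflict moves but does not go away.
- **The 10-subject look.** Two sections plan no such look, and no renal criterion is stated specifically for n = 10. This also stands, so the 3-of-10 case and the two-look figures are conditional. The n = 25 conflict does not depend on them.
- **Low expected toxicity.** This is a single dose, with renal disease, nephrotoxic drugs and diabetes excluded. At a true rate of 5% or less the conflict would seldom arise. But the documents support no particular rate, and a stopping rule exists for the case where toxicity is higher than hoped.
- **Human oversight.** The two later sections pause enrolment for the interim analyses, adverse events are reviewed in real time, and the medical monitor gives a written recommendation on continuing. This reduces the harm to subjects. It does not say which threshold governs.

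**Conclusion.** The concern holds. Three current sections of the same protocol version give two incompatible thresholds for one safety decision, and none is given precedence. With exactly 25 subjects in the renal denominator, the rules conflict at 6 and 7 events and nowhere else. The practical effect depends on a true event rate that the documents do not supply: negligible at 5% or below, substantial from about 15%. At 20%, there is roughly a one-in-four chance (27.4%) of an interim result that the pre-specified rule cannot settle. The point should be corrected before the rule is used.

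**What to change.** State one threshold, in the same words, in the front Statistical Analysis Plan, the monitoring plan's Data Analysis Plans and the Data Analysis section. Give it as a count at each look where it applies, and say whether a 10-subject look includes renal toxicity.

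- If the >20% rule is kept: halt at 6 or more of 25 (and 3 or more of 10, if used).
- If the 32% rule is kept: halt at 8 or more of 25 (and 4 or more of 10, if used).

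The choice belongs to the investigator and the medical monitor. Define the renal denominator, for example all treated subjects with both creatinine values, and give the percentage alongside the count in case that number is not exactly 25.

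As a minor tidy-up, report the interval for the chosen count with its level and method. Exact limits for 6/25 are 6.6%–51.4% (99%) and 5.2%–55.3% (99.7%). For 8/25 they are 11.3%–59.5% (99%) and 9.4%–63.2% (99.7%).

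The cost is a wording change to the protocol and its monitoring plan. No design element or data collection changes.
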